10.7.1. Peristomal skin lesions

Peristomal skin lesions are common and the incidences range from 20% to 50%.

Dermatoses included irritant reactions, particularly from leakage of urine or feces and pre-existing skin diseases, infections, allergic contact dermatitis, and pyoderma gangrenosum are less common. The classification of Borglund will be used to assess severity of the skin lesions the site. Photographs of the stoma and skin lesions will be taken as part of study documentation and for review by an independent panel if required.

Classification of peristomal skin complications (Borglund et al)

Category	Criterion	Additional explanation
E0/P0	No signs of irritative skin lesions; no obvious signs of erythema, erosion, or papular lesions	
E+/P0	Mild erythematous-erotic skin lesions E+/P0	This subgroup (E+) includes patients with dispersed papules lesions, and/or tiny, erythematous, macular lesions, vesicles, or tiny erosion.
E++/P0	Severe erythematous-erotic skin lesions.	The E++ subgroup includes patients with numerous papules and/or tiny macules, confluent erythematous macules, widely spread erosions, excoriations, and ulcerations.
E0/P+	Mild pseudoverrucous skin lesions	The mild (P+) pseudoverrucous skin lesion is characterized by dispersed, single, eruptive, or partly confluent, wart-like papules, or nodules located on the peristomal skin close to the mucocutaneous lining.
E0/P++	Severe pseudoverrucous skin lesions	The P++ reflects severe pseudoverrucous skin lesions and is a confluent, elevated ostomy circumference close to the ostomy mucosa.

10.8. Quality of Life Evaluation

Impact on quality of life will be evaluated by using two validated instruments EQ-5D-5L Quality of Life (QoL) questionnaire and Montreux Quality of Life questionnaire.

Secondary endpoints are:

CLINICAL INVESTIGATION PLAN

Change in quality of life from baseline at 8, 16, 24, 36 and 52 weeks post implantation will be assessed among subjects with the device *in situ*.

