4. STUDY OBJECTIVE AND ENDPOINTS

The primary objective is to evaluate the safety, performance and durability of the TIES® Port to 52 weeks in subjects after implantation. The secondary objective is to evaluate Quality of Life (QoL) in subjects implanted with the TIES® Port.

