5.3.4. Withdrawal

Early termination of study participation will be documented for patients that have signed an informed consent form and who exited for any of the following reasons:

- Subject for whom the implantation procedure has been attempted but cannot completed, for example, due to technical reasons. (These subjects will be followed for six months.)
- Subject who are explanted. (These subjects will be followed for six months.)
- Subject no longer wishes to continue with the study follow-up. No further follow up applies.
- Investigator believes it is the best medical interest of the subject to discontinue study participation due to safety reasons. (These subjects will be followed until study procedure related adverse events have resolved.)
- Death of the subject.

No additional subjects will be recruited to compensate for subjects who withdraw or are withdrawn from the study.

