6.13. Quality of Life (QoL) Questionnaires

Quality of Life questionnaires will be provided to the subjects, with instructions on how and when the questionnaires should be completed at baseline and from Visit 2 onwards. The QoL questionnaires can be completed either prior to the visit or during the office visit. These questionnaires can be filled in on the internet or on paper. Those QoL questionnaires include:

- EQ-5d quality of Life Questionnaire
- Montreux Quality of Life Questionnaire (specific to stomas)

See Appendix for more details on the QoL questionnaires.

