10. STATISTICAL CONSIDERATIONS

10.1. Objective of the study

This is a single-arm prospective multi-center clinical study to evaluate the safety, performance, durability of TIES® Port in patients who require permanent ileostomy as its

CLINICAL INVESTIGATION PLAN

primary objective, and assessment of impact on quality of life in the implanted patients as its secondary objective. Acceptability of the TIES® solution for patients will be part of assessment of performance.

For patients who require a permanent ileostomy, the current available alternatives for emptying of ileal contents are (1) attaching a stoma bag to the end-ileostomy; (2) surgery to create a pelvic pouch through an ileo-anal anastomosis; and (3) surgery to create a continent ileostomy. All of these procedures are associated with complications and failure rates.

The TIES® solution is intended as an alternative to stoma bags in patients requiring end-ileostomy so that the patient has control over emptying of intestinal wastes and to minimise the need to wear stoma bags for collection and emptying of intestinal wastes. This is achieved by putting a TIES® Lid on the TIES® Port to control emptying of intestinal waste through the Port, instead of letting the waste empty continuously into a stoma bag. In addition, the TIES® solution can also be an option for patients who cannot tolerate use of stoma bags due to complications, failed continent ileostomy or failed pelvic pouch.

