10.3. Study Population Definition

The study population is defined according to the Intent-to-Treat principle. All enrolled subjects will be taken into consideration in the reported results, without any planned exclusion.

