10.7. Safety Evaluation

Safety outcome measures are secondary endpoints and will be analysed as proportion of all implanted subjects using descriptive statistics. Safety information will be collected during the following intervals: during hospitalisation, interval from discharge to 4-weeks visit, interval after the 4-weeks visit including 8-weeks visit, interval after the 8-weeks visit including 16-weeks visit, interval after the 16-weeks visit including 24-weeks visit, interval after the 24-weeks visit including 36-weeks visit, and interval after the 36-weeks visit including 52-weeks visit.

Secondary endpoints are:

- Proportion of implanted subjects with treatment emergent adverse events. Treatment emergent adverse events are defined as events with onset during or after the implantation procedure.
- Proportion of implanted subjects with peristomal skin lesions will be evaluated using a validated 5-point scale by assessing signs of erythema, erosion, or papular lesions.
- Proportion of implanted subjects with device-related adverse event.
- Proportion of implanted subjects with device displacement, device revision or device replacement.

Photographs of the stoma are to be taken to document the ingrowth into the TIES® Port, surrounding peristomal skin and position of the implant at 4, 8, 16, 24, 36 and 52 weeks after implantation. At least 4 views are to be taken: horizontal, vertical frontal, vertical right and vertical left. Additional views may be required if skin lesions or device displacement develop.

The adverse events complicating end-ileostomy, continent ileostomy and pelvic pouch are well described in the literature. Adverse events known to complicate end-ileostomy include peristomal skin problems, infection, abscess, entero-cutaneous fistula, necrosis, stenosis, prolapse, retraction, parastomal hernia, incisional hernia, obstruction to emptying of intestinal contents. That said, the exact incidences are unknown because many reports are retrospective and the experience of the site may influence the outcomes.

All adverse events, device-related complications and device deficiencies or malfunctions described in section 4 will be fully summarized. Adverse events are to be assessed for seriousness and causality.

CLINICAL INVESTIGATION PLAN

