10.9. Statistical analysis

Statistical analyses will be done using SAS System®, Version 9.2 or further and a complete statistical analysis plan will be written before the conduct of analysis. All statistical analyses will be made on locked databases following data clarifications resolved due to Data Management process.

No replacement of missing data is planned in the statistical analysis.

No statistical testing will be conducted for any other parameters in the study and only descriptive analysis will be provided to fully describe the parameters recorded.

Continuous variables will be summarized using standard quantitative statistics: number of non-missing observations, mean, standard deviation, median, quartiles and range (minimum and maximum observed values). The number of missing observations will also be specified.

Categorical variables will be summarized using classical frequency statistics: number of non-missing observations and percentages by categories. Percentages will be calculated on the number of non-missing observations. The number of missing observations will also be specified.

Durability of use will be analysed using lifetable methods to allow for censoring due to subject withdrawal and device removals for reasons unrelated to device performance.

Two-sided 95% confidence intervals will be computed for all primary and secondary endpoints.

A statistical analysis plan will be written to describe all derived variables used in the reporting (especially for all parameters to be compared in time: EQ-5d and Montreux QoL questionnaire) and the statistical tables and listings to be generated.

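### Quality of life is summarised only in subjects who still have the Port, so the result for the one secondary objective is conditional on device retention

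*Combined protocol and SAP*

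**What the plan says.** Section 10.8 of the protocol defines the QoL endpoint as change from baseline, at 8, 16, 24, 36 and 52 weeks, which "post implantation will be assessed among subjects with the device" in situ. The synopsis and section 4.4 repeat the restriction.

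The objective is worded for a different set. Section 4 states: "The secondary objective is to evaluate Quality of Life (QoL) in subjects implanted with the TIES® Port". Section 10.1 describes "assessment of impact on quality of life in the implanted patients as its secondary objective".

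Other passages bear on the choice of set:

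- Section 10.3 declares intent-to-treat: "All enrolled subjects will be taken into consideration in the reported results, without any planned exclusion".
- Section 10.7 says that safety outcomes "will be analysed as proportion of all implanted subjects using descriptive statistics", while section 10.4 limits performance to subjects with the Port in situ.
- Section 5.3.4 lists explantation among the reasons for early termination, but adds: "Subject who are explanted. (These subjects will be followed for six months". It does not say what is assessed in that period. Section 6.17.2 says that no new data are collected once a subject has withdrawn.
- Section 6.13 provides for instructions on "how and when the questionnaires should be completed at baseline and from Visit 2 onwards". The two instruments are EQ-5D-5L and the stoma-specific Montreux questionnaire.
- Section 10.9 states: "No replacement of missing data is planned in the statistical analysis". QoL is descriptive, with two-sided 95% confidence intervals and no test.

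The protocol gives no QoL effect size, standard deviation or power.

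**The concern.** Section 10.6 treats removal or spontaneous loss of the Port as a durability event unless the removal is unrelated to device performance. Restricting QoL to subjects in situ therefore removes subjects, visit by visit, largely on the basis of an outcome of the device under study. If those subjects have poorer QoL change than the rest, the remaining mean is more favourable than the mean over everyone who received the implant.

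The reason for an in-situ set in section 10.4 does not carry over. Leakage around the Port cannot be observed once the Port is gone, but QoL can. The risk-benefit rationale in section 7.2 says that a patient can go back to ileostomy bags after removal. That patient still has a stoma and can complete both questionnaires.

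QoL is the only secondary objective, and section 7.2 lists improved QoL among the potential benefits. A reader of the final report will want to know what a patient can expect on receiving the implant. As planned, the report answers for patients who received it and kept it.

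**Working it through.** **1. Populations side by side.** The objective (sections 4 and 10.1) refers to implanted subjects. The endpoint (synopsis, 4.4 and 10.8) refers to subjects in situ at the visit. Section 10.3 refers to all enrolled subjects, whom section 5.3.1 defines as those who signed consent. A subject whose Port was removed has been implanted and enrolled but is not in situ, and so leaves the QoL analysis from that point. No supplementary QoL analysis brings such subjects back. Section 10.9 promises a separate analysis plan, but describes it as covering derived variables, tables and listings, not a different population.

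**2. The plan's own figures.** None is stated for QoL. The nearest is the evaluable share in section 10.5: at least 160 of 200 (80%) at 24 weeks, with 79% power for the leakage endpoint if the true proportion is 70%. That cell reproduces with a normal approximation:

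Φ[(0.70 − 0.60)/√(0.70 × 0.30/160) − 1.96] = Φ(2.76 − 1.96) = Φ(0.80) = 78.8%.

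All 30 cells of the table reproduce in this way to within 0.5 points. The QoL point neither depends on the table nor changes it; only the 80% is used below, as a proxy.

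**3. Formula.** Let p be the share of implanted subjects in situ at a visit, and let M_in and M_out be the mean changes of subjects in situ and not in situ. Then

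M_all = p × M_in + (1 − p) × M_out,

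M_in − M_all = (1 − p) × (M_in − M_out) = (1 − p) × d.

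**4. Inputs.** The documents do not give d; 0.2 to 1.0 SD is assumed. For p there are three anchors. Section 1.5 reports, for 11 subjects, implants in situ beyond 6 months in 10 and beyond 12 months in 5. Section 10.5 gives the 80%.

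**5. Results**, for 200 implanted subjects:

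| p | Not in situ | d = 0.2 | d = 0.5 | d = 1.0 |
|---|---|---|---|---|
| 10/11 (earlier studies, 6 months) | 18 | 0.02 SD | 0.05 SD | 0.09 SD |
| 80% (evaluable share, proxy) | 40 | 0.04 SD | 0.10 SD | 0.20 SD |
| 5/11 (earlier studies, 12 months) | 109 | 0.11 SD | 0.27 SD | 0.55 SD |

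If d is zero there is no distortion. If d is negative, the in-situ mean understates the all-implanted mean.

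**6. What six months of follow-up can supply.** Six months is about 26 weeks. A Port removed at week 10 is followed to about week 36, which covers the 16-, 24- and 36-week questionnaires but not the 52-week one. In general, a Port removed before about week 26 (52 − 26) yields no 52-week QoL.

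**The case against.** The strongest reply is that a summary among subjects who keep the device is a legitimate quantity, openly stated and purely descriptive. Durability is reported at the same five timepoints, so attrition can be seen beside the QoL results. This stands as a reason to keep the in-situ summary. It does not make that summary an answer for implanted subjects.

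The protocol also uses the word implanted loosely: section 10.4 limits performance to subjects in situ and then counts Lid users among implanted subjects. This weakens any claim of a flat contradiction with the objective. However the objective is read, explanted subjects still appear in no QoL result.

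Three stronger readings are tempting, and the documents do not support them.

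- A reader might infer a breach of intent-to-treat. Section 10.3 concerns enrolled subjects, so an all-implanted set would not satisfy it either. It asks only that they be considered in the reported results, and explanted subjects do appear under durability and safety. Section 10.3 needs aligned wording; it does not by itself establish the implanted set.
- A reader might infer that benefit is certainly overstated, or that the retained group must improve by selection. No document reports QoL after explantation. Baseline is pre-operative and some subjects enter with a failing stoma or pouch, so an explanted subject could still gain. Some removals are unrelated to the device.
- A reader might take 40% as a possible explant share, from the 120-subject column in section 10.5. That column concerns assessability for the 24-week leakage endpoint, which may also be lost for reasons other than explantation.

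**Conclusion.** The point holds as one about the analysis set. The planned QoL mean and confidence interval describe subjects who retain the Port, while the objective is worded for implanted subjects, and nothing in the plan fills the gap.

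The size depends on two unknowns. With d assumed between 0.2 and 1.0 SD, the overstatement runs from 0.02 SD (p = 10/11) to 0.55 SD (p = 5/11), and from 0.04 to 0.20 SD at the 80% proxy. The two earlier-study shares come from 11 subjects, some with hernias of a kind now excluded, so they mark a range and do not predict retention here. The favourable direction is plausible but not demonstrated.

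No error rate, success criterion or sample size is affected, because QoL is descriptive. A change is still warranted: the data can be collected, and this is the only secondary objective.

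**What to change.** - In sections 4.4 and 10.8 (and the synopsis), make all implanted subjects with available QoL the main analysis set. Keep the in-situ summary as supplementary, labelled as conditional on retention.
- Collect both questionnaires at the scheduled visits that fall within the existing six-month follow-up of explanted subjects. Reconcile section 5.3.4 with section 6.17.2 so that this collection is allowed.
- At each visit, report the numbers implanted, in situ and contributing QoL.
- State that 52-week QoL will be missing for early explants. Since no imputation is planned, add a simple sensitivity analysis for them, such as a range of assumed changes that includes gains as well as losses.
- Align the enrolled wording of section 10.3 with the implanted set.

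The cost is two questionnaires at existing follow-up contacts, some extra tables and a mean that may be less favourable. The 52-week result will still be incomplete for early explants, which is why the counts and the sensitivity analysis are needed.

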10.9. Statistical analysis

Statistical analyses will be done using SAS System®, Version 9.2 or further and a complete statistical analysis plan will be written before the conduct of analysis. All statistical analyses will be made on locked databases following data clarifications resolved due to Data Management process.

No replacement of missing data is planned in the statistical analysis.

No statistical testing will be conducted for any other parameters in the study and only descriptive analysis will be provided to fully describe the parameters recorded.

Continuous variables will be summarized using standard quantitative statistics: number of non-missing observations, mean, standard deviation, median, quartiles and range (minimum and maximum observed values). The number of missing observations will also be specified.

Categorical variables will be summarized using classical frequency statistics: number of non-missing observations and percentages by categories. Percentages will be calculated on the number of non-missing observations. The number of missing observations will also be specified.

Durability of use will be analysed using lifetable methods to allow for censoring due to subject withdrawal and device removals for reasons unrelated to device performance.

Two-sided 95% confidence intervals will be computed for all primary and secondary endpoints.

A statistical analysis plan will be written to describe all derived variables used in the reporting (especially for all parameters to be compared in time: EQ-5d and Montreux QoL questionnaire) and the statistical tables and listings to be generated.

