10.5. Sample size

The purpose of the study is to assess the durability and performance of the TIES® Port over one year. The table below shows the power to demonstrate non-inferiority to within 10% of the target 24-week performance criterion of 70% of subjects with the device *in situ* experiencing no leakage (i.e. lower two-sided 95% confidence limit no less than 60%) according to the true proportion and number of assessable subjects.

True proportion experiencing no leakage at 24 weeks	200 subjects	180 subjects	160 subjects	140 subjects	120 subjects
70%	87%	83%	79%	73%	67%
71%	93%	90%	87%	82%	76%
72%	97%	95%	92%	89%	83%
73%	99%	98%	96%	93%	89%
74%	99%	99%	98%	97%	94%
75%	100%	100%	99%	98%	97%

CLINICAL INVESTIGATION PLAN

There will be sufficient power with the planned 200 subjects to demonstrate non-inferiority of the TIES® Port with respect to the primary performance criterion (efficacy when device used as intended), if at least 80% of subjects are evaluable at 24 weeks (i.e. with at least 160 subjects). If the true proportion of patients experiencing no leakage is higher than the expected minimum of 70% there will be sufficient power to demonstrate non-inferiority even with fewer than the expected proportion of evaluable subjects at 24 weeks.

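### QoL change is averaged over non-missing questionnaires only, so the five visit means come from different subjects and hold only if non-return is unrelated to QoL

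*Combined protocol and SAP*

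**What the plan says.** Section 10.8 makes "Change in quality of life from baseline at 8, 16, 24, 36 and 52 weeks post implantation" a secondary endpoint for EQ-5D-5L and Montreux, and says that it "will be assessed among subjects with the device" in situ.

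Section 10.9 gives the only rule for missing values: "No replacement of missing data is planned in the statistical analysis". Continuous variables are described on the non-missing observations, and "The number of missing observations will also be specified". Two-sided 95% intervals are promised for all primary and secondary endpoints, while everything apart from the primary endpoint is to be described and not tested. The SAP still to be written is to define derived variables, "especially for all parameters to be compared in time: EQ-5d and Montreux QoL questionnaire".

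No section adds a repeated-measures model, a same-subject comparison or a sensitivity analysis for QoL. For durability, by contrast, 10.9 uses lifetable methods so that withdrawal is allowed for.

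**The concern.** Some questionnaires will be missing. Section 6.17.2 stops all data collection at withdrawal. Section 6.17.1 declares loss to follow-up only after three consecutive missed visits, so gaps can arise before that.

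Under 10.9 each visit mean describes whoever answered at that visit. If subjects with a low score are less likely to answer next time, those remaining at week 52 are a selected group, and the average change can drift although the true average does not. The interval is then centred in the wrong place. The earlier scores of those who stopped would predict the missing ones, but they are not used.

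QoL is the study's one secondary objective (section 4) and there is no control arm. The course over time is therefore the evidence on QoL, and readers will interpret it even though no test is attached.

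**Working it through.** **1. The plan's own figures.** Section 10.5 gives power for the primary endpoint only. It is reproduced by Φ((p − 0.60)/√(p(1 − p)/n) − 1.96). With p = 0.70:
- n = 200: 0.10/√(0.21/200) = 3.09; 3.09 − 1.96 = 1.13; power 87%, as stated.
- n = 160: 0.10/√(0.21/160) = 2.76; 2.76 − 1.96 = 0.80; power 79%, as stated.

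The present point does not touch these figures. There is no QoL figure to reproduce.

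**2. Inputs.** From the documents: 200 subjects, baseline and five QoL visits, non-missing observations only. Assumed, because the documents are silent:
- scores with SD 1 at every visit, and a true mean change of 0.25 SD at all five visits;
- post-operative scores correlating 0.6-0.7 with each other and 0.3-0.5 with baseline (unequal case), or all correlations equal at 0.4-0.7;
- a subject who stops answering does not resume, and is more likely to stop after a low previous score (logit slope 0.5 or 1.0 per SD);
- about 15-20% missing at week 24 and about 30% at week 52.

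**3. Direction of the error.** Let ρp be the correlation between two post-operative scores, ρb that of a post-operative score with baseline, and z a standardised score. For a later visit k:
- given an earlier post-operative score, E[Yk − Y0 | z] = 0.25 + (ρp − ρb)z;
- given the baseline score, E[Yk − Y0 | z0] = 0.25 − (1 − ρb)z0.

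Subjects who keep answering have z above zero on average. If week 8 is complete, so that non-return depends only on post-operative scores, the error has the sign of ρp − ρb: upward when ρp exceeds ρb, and zero when they are equal. If non-return already starts at week 8, it depends on the baseline score, and the second line adds a downward pull.

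**4. Simulated size at week 52 (true value 0.25 SD).**

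| Setting | Observed-case mean | Coverage of 95% interval |
|---|---|---|
| Week 8 complete, ρp > ρb | 0.26-0.37 | 76-95% |
| Same, missingness about halved (9% at week 24, 16% at week 52) | 0.26-0.31 | 89-94% |
| Non-return from week 8, ρp > ρb | 0.24-0.31 | 92-95% in runs spanning 0.24-0.30 |
| Week 8 complete, equal correlations | about 0.25 | no bias |
| Non-return from week 8, equal correlations | 0.215-0.241 | not tabulated |

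A likelihood estimate using all observed visits stayed at 0.25 SD throughout. Where ρp > ρb its standard error was about 5-9% smaller.

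**5. Scale against precision.** With 30% missing, n = 140 and the standard error is √(2(1 − ρb))/√140, which is 0.085 at ρb = 0.5 and 0.100 at ρb = 0.3. The largest error, 0.37 − 0.25 = 0.12, is 0.12/0.100 = 1.2 standard errors. Expected coverage is then Φ(1.96 − 1.2) − Φ(−1.96 − 1.2) = 78%, close to the simulated low of 76%. The smallest upward error, 0.01, is about 0.1 standard error.

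**6. What a likelihood model leaves.** A second model set the true mean change to 0 and tied non-return to the change itself, with between-subject SD of change 0.5-1.0 and 20-40% missing at week 52. If non-return depended on the previous, observed value, the observed-case error at week 52 was +0.12 to +0.57 SD and the likelihood estimate was 0.00. If it depended on the current, unseen value, the errors were +0.16 to +0.63 and +0.09 to +0.22 SD. This model is used only to compare the two methods, not to size the problem.

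**7. A limit.** If every subject's own change is exactly zero, the mean change from baseline is zero whoever stops answering. The drift needs subjects to differ in their change.

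**The case against.** **Size.** A reader might take the non-return rate from 10.5, where power is called sufficient "if at least 80% of subjects are evaluable at 24 weeks". That figure concerns evaluability for the leakage criterion among subjects with the Port in situ, so it can include explants. It is not a QoL rate. Sections 6.9 and 6.13 also work against non-return: questionnaires may be completed before or during visits, online or on paper; sites check completion from week 16; and the last two visits may be by video. This stands, and the size above is illustrative.

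**Direction.** A reader might infer that the plan will manufacture a growing benefit. The documents do not support that. The upward results need post-operative scores that agree more with each other than with baseline, and they are largest when week 8 is nearly complete. Otherwise the error can be nil or downward.

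**Status.** QoL is descriptive, carries no success criterion, and missing counts will be reported. It would be wrong to say that missing data are passed over in silence. But a count discloses the problem without correcting the mean, and a 95% interval is an inferential statement even without a test.

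**The remedy.** The endpoint is defined in situ. A repeated-measures model applied without care would carry a subject explanted at week 30 forward to weeks 36 and 52 as if the Port were still there. This stands and shapes the fix. How the in-situ set fits with 10.3 ("All enrolled subjects will be taken into consideration in the reported results, without any planned exclusion") is a separate question that the model does not settle.

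**Conclusion.** The point holds as a limited one. Section 10.9 fixes an available-case summary for a within-subject course over five visits and attaches intervals to it. That summary needs non-return to be unrelated to QoL, and nothing elsewhere relaxes this.

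Under the stated assumptions the week-52 mean lies between about 0.21 and 0.37 SD for a true 0.25 SD: from about 0.04 SD too low to 0.12 SD too high, against a standard error of roughly 0.08-0.10. Neither size nor sign can be derived from the documents. A likelihood analysis needs only that non-return be explained by observed scores, which is a weaker assumption, and it was unbiased in every setting where that was true. The consequence is confined to the QoL results.

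**What to change.** In 10.9 and the SAP, for each QoL score:
- Add a mixed model for repeated measures of change from baseline at weeks 8, 16, 24, 36 and 52, with visit, baseline score and baseline-by-visit as fixed effects and an unstructured covariance. Report model means and 95% intervals at each visit. The model fills in no values, so it is consistent with the no-replacement rule.
- Keep the planned observed-case table, with numbers missing, beside it.
- State that the model covers questionnaires missing while the Port is in situ. Say explicitly how visits after explant are treated, for example by reporting them separately, so that explanted subjects are not projected as if still in situ.
- Add a delta-adjusted sensitivity analysis, because some bias remains if non-return depends on the unseen score.

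The cost is SAP wording, one standard SAS procedure and modest extra programming. No new data are needed. The downside is reliance on missing at random, which is still less than the planned summary assumes.
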